### a. Primary study parameter(s)

The primary outcome, QoR-15 at day 1, 4 and 7, will be compared among patients randomized to either the intervention and control group, using Student's t-test or a nonparametric Mann Whitney U test.

Mixed effects linear regression models will be conducted to investigate the effect of the smartphone app on QoR-15 over the first week post discharge as a function of the randomization assignment (i.e. intervention vs control), time (i.e. measurements before surgery, and at day 1, 4 and 7 post discharge), and their interaction term. Random effects, i.e. random intercept, will be fitted per individual to account for clustering effects. To adjust for practice variation between the participating hospitals, the factor hospital will be added as fixed effect to the mixed model. In addition, we will perform a sensitivity analysis if the results of the mixed model analysis indicate for bias.

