## SUMMARY

**Rationale:** To date the majority of surgical interventions is performed in day care and patients are being discharged soon after the first critical postoperative period. At home, patients have limited options to contact the hospital in case of severe pain and nausea. We have provided day care surgical patients with a smartphone application for remote monitoring that is configured to self-record postoperative pain and nausea after being discharged from hospital. Furthermore, it provides a messaging service to contact the hospital in case of (severe) pain or nausea. Despite the promising initial patient experiences of such an application, we do not know whether remote monitoring with a smartphone application improves the patient's experience during the recovery period.

**Objective:** To evaluate the experienced quality of recovery after day care surgery between patients provided with a smartphone application for remote monitoring and patients receiving standard of care (no remote monitoring).

**Study design:** (Non-blinded) randomized controlled trial with mixed methods design

**Study population:** Adult patients (aged 18 years or older) scheduled for day care surgery

**Intervention (if applicable):** The intervention group receives the smartphone application for remote monitoring during weekdays from 8 am to 17 pm up to 7 days after surgery. With this application, patients are able to record experienced pain and nausea. In addition, they can send messages to the hospital. Daily monitoring is performed by an anaesthesia professional who will contact the patient in case severe pain or nausea is reported in the app. The control group receives standard of care (with post-discharge verbal and paper instructions).

**Main study parameters/endpoints:** The main study endpoint is the difference between patients using remote monitoring and patients not using remote monitoring in perceived quality of recovery measured with the QoR-15 questionnaire on the 7th day after day care surgery. Secondary endpoints are 1) the overall score on the Quality of Recovery-15 at day 1, 4 and 7 post discharge, 2) the perceived quality of hospital aftercare and 3) experienced psychological effects of remote monitoring during postoperative recovery from day care surgery.

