## 2. OBJECTIVES

### a. Primary Objective

b. Primary outcome is to assess the difference between patients using remote monitoring and patients not using remote monitoring in perceived quality of recovery measured with the QoR-15 questionnaire on the 7th day after day care surgery.

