**d. Sample size calculation**

An 8.0 difference in the overall score in the QoR-15 questionnaire on postoperative day 7 is considered a minimal clinically relevant difference (16) with standard deviation of 19.1 (17). Group sample sizes of 91 patients achieve 80% power to detect a difference of -8.0 with a significance level (alpha) of 0,05 using a two-sided two-sample t-test. *Sample Size calculation is performed with PASS 2021 Power Analysis and Sample Size Software (2021). NCSS, LLC. Kaysville, Utah, USA, [ncss.com/software/pass](http://ncss.com/software/pass).* We plan to include 20% extra patients to adjust for dropout or incomplete data. Total sample will be 230 subjects divided into two groups.

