## 7. METHODS

### a. Study parameters/endpoints

#### i. Main study parameter/endpoint

Quality of recovery measured with the Quality of Recovery questionnaire-15 (QoR-15) (16, 24) at day 7 post discharge between patients with remote monitoring (intervention group) and patients without remote monitoring (non-intervention group) after day care surgery.

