#### ii. Secondary study parameters/endpoints (if applicable)

Quality of recovery measured with the quality of recovery questionnaire-15 (QoR-15) (16, 24) at post discharge day at post discharge day 1, 4 and 7.

Postoperative Pain: Experienced postoperative pain (POP) measured with (in-app) NRS for Pain (25) (combined with 11 faces scale) measured at day 1, 4 and 7 post discharge.

Post discharge nausea and vomiting: Experienced post discharge nausea and vomiting (PDNV) measured with the Myles' PDNV assessment scale (21) between intervention and non-intervention group. Measured at day 1, 4 and 7 post discharge.

Medication Dosage and Use: the total dosage of administered analgesics will be assessed during hospital stay and recorded in the medical record. The total dosage of administered analgesics at home after discharge will be assessed by asking patients to indicate which pain medication they have been using. Measured at day 1, 4 and 7 post discharge.

The number of contacts with the hospital, general practitioner or emergency department. All types of contacts (e.g. physically, e-mail, telephone) will be assessed by reviewing the PDMS for registered contacts and by asking the patients to indicate the number of contacts.

Measured at day 1, 4 and 7 post discharge.

The number of surgical complications assessed according to the Clavien Dindo classification of surgical complications (26, 27) will be assessed by reviewing the PDMS and by asking the patients to indicate the number of complications. Measured at day 1, 4 and 7 post discharge.

The number of readmissions. A readmission is defined as an admission to hospital or emergency department for medical care or observation regarding their surgical intervention. Readmissions will be assessed by reviewing the PDMS and by asking the patient to indicate the number of readmissions. Measured at day 1, 4 and 7 post discharge.

Satisfaction: Patients' satisfaction with the provided care will be assessed using a 1-item self-created VAS scale ('not at all to very much', 0-10 range). Satisfaction will be measured at day 1, 4 and 7 post discharge.

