## 9. STATISTICAL ANALYSIS

All statistical analyses will be conducted according to the intention-to-treat principle (31, 32) considering all patients in the treatment groups to which they were randomly assigned, excluding cases lost to follow-up due to withdrawal of consent or cancellation of surgery. Continuous distribution of the data will be assessed by visual inspection of histograms and normality tests. For both study arms, the baseline characteristics will be reported for the intervention and control group and expressed as counts and percentages, means and standard deviations (SD), or medians and interquartile ranges (IQR) whenever appropriate. Baseline characteristics of patients with and without complete follow up will be compared to examine whether selective dropout occurred. Analyses will be performed using IBM SPSS Statistics for Windows, Version 22.0. Armonk, NY: IBM Corp.

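### Section 9.a calls QoR-15 on days 1, 4 and 7 the primary outcome, against a day-7 primary endpoint elsewhere, and does not say which test or model term decides

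*Combined protocol and SAP*

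**What the plan says.** Three places define a single primary time point. The Summary and the Primary Objective in Section 2 refer to "perceived quality of recovery measured with the QoR-15 questionnaire on the 7th day after day care surgery", and Section 7.a.i gives "Quality of recovery measured with the Quality of Recovery questionnaire-15 (QoR-15) (16, 24) at day 7 post discharge". The sample size section assumes an 8.0-point difference on day 7 and an SD of 19.1, with "a significance level (alpha) of 0,05 using a two-sided two-sample t-test".

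The set of days 1, 4 and 7 is listed as secondary. The Summary says: "Secondary endpoints are 1) the overall score on the Quality of Recovery-15 at day 1, 4 and 7 post discharge". Section 7.a.ii has the same entry: "QoR-15) (16, 24) at post discharge day at post discharge day 1, 4 and 7". Day 7 therefore appears under both labels.

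Section 9.a then says: "The primary outcome, QoR-15 at day 1, 4 and 7, will be compared among patients randomized to either the intervention and control group". The comparison is to be by t-test or Mann-Whitney test. Under the same heading comes a mixed model with arm, "time (i.e. measurements before surgery, and at day 1, 4 and 7 post discharge), and their interaction term", a random intercept per patient, and hospital as a fixed effect. Section 9.b has no entry for QoR-15.

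**The concern.** There are two faults in the paragraph that governs the primary analysis.

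1. **The label.** The three-day set that the Summary and Section 7.a.ii call secondary is called primary in Section 9.a.
2. **The ranking.** Neither the two-group test nor the mixed model is called primary, supportive or secondary. No coefficient or contrast of the model is named as the treatment effect.

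The stated alpha of 0.05 and power of 80% belong to one day-7 t-test. The model offers several quantities: a between-arm difference on day 7, a difference in change from the preoperative score, an overall interaction test, and an average arm effect. Only the first answers the day-7 question. If these disagree, the plan does not settle whether the trial met its primary endpoint. The trial is unblinded with a patient-reported outcome, so the deciding analysis should be fixed before the data are seen.

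**Working it through.** **Inputs.** From the sample size section: difference 8.0, SD 19.1, 91 per arm, two-sided alpha 0.05, total 230. From Section 9.a: four time points (preoperative, days 1, 4 and 7), random intercept. The documents give no between-day correlation, so r = 0.3, 0.5 and 0.7 are assumed. Complete data, no hospital effect and equal allocation are also assumed.

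**Plan's own figure.** The standard error of the day-7 difference is 19.1 × √(2/91) = 2.83, so the noncentrality is 8/2.83 = 2.83. Noncentral-t power is 79.8% at 90 per arm and 80.2% at 91. The plan's 91 per arm reproduces. Allowing for 20% dropout, 182/0.8 gives 228, close to the stated 230.

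**Interaction term, day 7 against preoperative score.** Its standard error is 2.83 × √(2(1 − r)).
- r = 0.3: 3.35, ratio 8/3.35 = 2.39, power 66.4%
- r = 0.5: 2.83, ratio 2.83, power 80.5%
- r = 0.7: 2.19, ratio 3.65, power 95.4%

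Its correlation with the day-7 statistic is √((1 − r)/2) = 0.59, 0.50 and 0.39, so the two tests can easily disagree.

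**Overall interaction, 3 degrees of freedom.** Take arm differences of 0, 2.7, 5.3 and 8 at the four time points. The noncentrality is Σ(d − mean d)² / [(2 × 19.1²/91)(1 − r)] = 35.6/[8.02(1 − r)] = 6.3, 8.9 and 14.8. Power is 53.9%, 70.1% and 91.1%.

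**Model's day-7 between-arm contrast.** Simulated power is 80.1%, 80.3% and 81.2%.

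**Disagreement with the day-7 t-test on significance** (20,000 simulated trials per setting, same effect pattern):

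| Candidate result | r = 0.3 | r = 0.5 | r = 0.7 |
|---|---|---|---|
| Model day-7 between-arm contrast | 2.0% | 1.8% | 1.4% |
| Day 7 against preoperative score | 26.6% | 22.5% | 19.6% |
| Overall 3-df interaction | 37.4% | 28.9% | 21.2% |

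**Average arm effect over all four time points.** If the 8-point effect is present on day 7 only, power is 17.6%, 14.5% and 12.6%.

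**Error under the null.** Each test alone is close to 5% (4.8% to 5.4% in simulation). Counting success on either the day-7 test or the day-7 interaction term gives about 9% at all three correlations.

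**Literal three-day reading.** If any one of three day-wise tests sufficed, error would be 1 − 0.95³ = 14.3% at zero correlation, 12.5% at 0.5 and 8.4% at 0.9. The plan states no such rule.

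**t-test or Mann-Whitney.** Choosing by a normality test on day-7 residuals kept null error at 4.9% to 5.4% in 10,000 trials per setting, including data with a ceiling at 150.

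**The case against.** The strongest reply is that the intention can be inferred. Day 7 is the only primary time point in the Summary, Section 2 and Section 7.a.i. The trial is sized on a day-7 t-test, and Section 9.a mentions the t-test first. The mixed model is introduced for the course over the week, which fits the secondary QoR-15 endpoint, and the same model is used for secondary outcomes in Section 9.b. Because 9.b has no QoR-15 entry, 9.a probably merges the primary and secondary analyses.

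That stands for the endpoint. It does not settle the analysis. A sample size basis does not rank analyses, and 9.a neither limits the t-test to day 7 nor makes the model subordinate. The model also has a fair claim to be primary, since it alone adjusts for hospital, the stratification factor in Section 7.b.

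The size can also be challenged. Disagreement at the design effect is not an error rate: two independent tests with 80% power would disagree in 2 × 0.8 × 0.2 = 32% of trials. Section 9.d expects minimal losses, and with all 115 per arm analysed the t-test has 88.5% power and disagreement with the change contrast falls to about 20%, 15% and 12%. Both points are right, and the smaller figures are still material. The model's day-7 contrast agrees with the t-test in about 98% of trials, so the problem arises only if another term is taken as primary. Section 9.a leaves that open.

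The t-test or Mann-Whitney choice is minor. Section 9 says: "Continuous distribution of the data will be assessed by visual inspection of histograms and normality tests". Section 9.b states the fallback for other outcomes; 9.a simply omits it.

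**Conclusion.** The concern holds. Section 9.a contradicts the Summary and Sections 2, 7.a.i and 7.a.ii on what is primary, and it names no deciding analysis or model term. The sample size is not affected: 91 per arm gives 80.2% power for the day-7 t-test.

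At the design effect, the unranked alternatives give a different verdict from that t-test in roughly 20% to 37% of trials at 91 per arm. Choosing afterwards between the day-7 test and the change contrast would raise the error to about 9%. These figures rest on the assumed correlations of 0.3 to 0.7, complete data and, for the 37%, an effect that grows to 8 points by day 7. The 8% to 14% family-wise error applies only under an any-day rule that the plan does not contain, and carries no weight here. The point must be fixed because it decides which result is confirmatory.

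**What to change.** In Section 9.a, state that the primary outcome is QoR-15 on day 7 only, that the primary analysis is the two-sample t-test of the between-arm difference on that day at two-sided alpha 0.05, and that all other QoR-15 analyses are secondary or supportive. Move days 1 and 4 and the course over the week to Section 9.b. Either fix the deciding test in advance or tie any Mann-Whitney fallback to the distribution check in Section 9.

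If the sponsor prefers the mixed model because it adjusts for hospital, name its day-7 between-arm contrast as the sole primary result and restate the power basis in the sample size section.

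With the t-test the cost is wording only: N, alpha, power and data collection are unchanged. With the model contrast the power statement must also be rewritten, though power stays near 80% at 91 per arm under the assumptions above. Two downsides follow. A significant result on day 1 or 4, or in a supportive analysis alone, can no longer be called a primary success. An unadjusted t-test leaves the hospital adjustment to the supportive model.

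### The day-7 QoR-15 t-test is valid and adequately powered, but Section 9.a names no single decisive analysis and its two-sample test leaves baseline QoR-15 and hospital unused

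*Combined protocol and SAP*

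**What the plan says.** Section 2 sets the primary outcome as recovery "measured with the QoR-15 questionnaire on the 7th day after day care surgery". The Summary and Section 7.a.i agree on day 7, and the sample size calculation is for day 7: "Group sample sizes of 91 patients achieve 80% power to detect a difference of -8.0", with SD 19.1 and a two-sided two-sample t-test at 0.05. Section 7.a.ii lists QoR-15 "at post discharge day at post discharge day 1, 4 and 7" as secondary.

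Section 9.a reads differently: "The primary outcome, QoR-15 at day 1, 4 and 7, will be compared among patients randomized", the comparison being made "using Student's t-test or a nonparametric Mann Whitney U test". Under the same heading it adds a linear mixed model with a random intercept per patient and terms for arm, "time (i.e. measurements before surgery, and at day 1, 4 and 7 post discharge), and their interaction term". For that model only, "the factor hospital will be added as fixed effect to the mixed model".

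Other sections bear on this:
- The opening of Section 9 says distributions will be examined with histograms and normality tests. Section 9.b, for several secondary endpoints, uses Mann-Whitney when data are not normal.
- Section 7.b stratifies randomisation by hospital.
- Section 9.d plans multiple imputation.
- On the pre-surgery QoR-15, the Summary asks both arms for it one day before admission, while Section 4.a ties it to a telephone call two days before. Section 7.c sends the app invitation to the intervention arm two days before admission, yet has randomisation follow consent, with the signed form brought on the admission day.

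**The concern.** Three analyses sit under the primary heading: t-test, Mann-Whitney and mixed model. They can disagree, and the plan does not say which one counts or which mixed-model coefficient would be read. The wording also promotes days 1 and 4 to primary status, against the sections that define the endpoint.

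The analysis that sized the trial also ignores two things the trial collects or builds in: each patient's own pre-surgery score and the stratification factor. The mixed model includes hospital but treats the pre-surgery score as one more outcome rather than as a covariate. At stake are a clear primary result and, to an extent the documents do not let us fix, the width of its confidence interval.

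**Working it through.** **Inputs.** Difference 8.0, SD 19.1, two-sided alpha 0.05, 91 per arm, 20% loss and 230 in total come from the sample size calculation. The baseline to day-7 correlation (ρ) and the share of variance explained by hospital are not in the documents; the values below are assumptions.

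**1. The plan's own figure.** Standard error = 19.1 × √(2/91) = 2.83. Noncentrality = 8.0/2.83 = 2.83. With 180 df, noncentral-t power is 80.2%; at 90 per arm it is 79.8%, so 91 is correct. For dropout, 182/0.80 = 227.5, which 230 covers. If 20% are lost, 184 remain (92 per arm, power 80.7%). With no loss (115 per arm) power is 88.5%.

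**2. Baseline-adjusted day-7 difference.** Residual SD = 19.1 × √(1 − ρ²), with 2n − 5 df (arm, baseline and two hospital terms). No variance is credited to hospital here. Half-width = t × residual SD × √(2/91); for the t-test it is 5.59 points.

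**3. Mixed-model arm-by-day-7 term read as a change from baseline.** With equal SDs at both times, SD of change = 19.1 × √(2 − 2ρ), with 180 df.

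| ρ (assumed) | Residual SD | Adjusted power, 91/arm | 95% CI half-width, 91/arm | Adjusted power, 115/arm | Change-term power, 91/arm |
|---|---|---|---|---|---|
| 0.1 | 19.00 | 80.6% | 5.56 | 88.8% | 55.4% |
| 0.3 | 18.22 | 83.8% | 5.33 | 91.2% | 66.1% |
| 0.5 | 16.54 | 90.1% | 4.84 | 95.5% | 80.2% |
| 0.7 | 13.64 | 97.6% | 3.99 | 99.3% | 95.2% |

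The unadjusted t-test has 80.2% at 91 per arm and 88.5% at 115. The change term equals it at ρ = 0.5, where √(2 − 2ρ) = 1, and is weaker below that. So it matters which coefficient is read. The model's other natural contrast, the arm difference at day 7, equals the raw day-7 difference when data are complete, apart from hospital.

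**4. Hospital alone.** Residual SD = 19.1 × √(1 − R²). At 91 per arm, power is 80.6%, 82.2% and 84.2% if hospital explains an assumed 1%, 5% and 10% of variance.

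**5. Missing baselines.** If patients without a baseline were dropped, the variance factor would be (1 − ρ²)/(1 − m), with m the missing share. The gain is cancelled at m = ρ²: 1%, 9% and 25% for ρ = 0.1, 0.3 and 0.5. Baselines therefore need imputing, not deletion.

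**6. Baseline timing.** The app invitation two days before admission implies that allocation is known by then. A questionnaire completed one day before admission would follow it. A signed form handed over on the admission day, with randomisation after consent, would instead put baseline before allocation. Both readings are open. With equal SDs, each point by which knowledge of allocation shifts one arm's baseline moves the adjusted estimate by ρ points, for example 0.5 point at ρ = 0.5.

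**The case against.** **The choice of test is guided.** A reader might infer that the t-test or Mann-Whitney wording lets the analyst keep whichever result is significant. The documents do not support that. The opening of Section 9 and the explicit rule in Section 9.b point to a choice by distribution, although 9.a does not repeat the rule and no cut-off is given. A simulated switch (Shapiro-Wilk at 0.05 on residuals, 91 per arm, 6,000 trials) gave false-positive rates of 5.0% for normal scores and 5.1% and 4.9% for two skewed gamma shapes. A further simulation gave about 4.4% to 5.2%. Error is not materially inflated. What remains is that Mann-Whitney does not estimate the 8.0-point mean difference behind the sample size.

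**Day 7 is fixed elsewhere.** A reader might also infer three co-primary days, with a false-positive rate of about 11% to 14% if any one sufficed (correlations 0.7 to 0.3). No section plans such a claim, and the other sections support inferring a day-7 t-test. This narrows the point to a conflict in 9.a but does not remove it, because the mixed model's role and contrast stay undefined.

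**The gain may be small.** This stands. Section 9.d expects little loss, and at 115 per arm the t-test already has 88.5%. At ρ = 0.3 the gain is then 91.2 − 88.5 = 2.7 percentage points.

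**Planned imputation helps the t-test too.** This also stands. With 20% of day-7 scores missing and ρ = 0.5, imputing from arm and the other visits gives the t-test a standard error of about 2.72, close to the planned mixed model's 2.71. Baseline adjustment using only the observed day-7 scores gives 2.44, so a gap remains.

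**Conclusion.** The point holds as one of clarity first and precision second. Section 9.a conflicts with the Summary, Section 2, the sample size calculation and Section 7.a.i on the primary time point, and with Section 7.a.ii on the status of days 1 and 4. It does not say whether the two-sample test or the mixed model, or which contrast, decides the trial. That is what makes the change worth requiring.

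The unused baseline and hospital information is a near-free improvement of unknown size: at 91 per arm, 0.4 percentage points of power at ρ = 0.1, 3.6 at 0.3 and 9.9 at 0.5. These figures assume SD 19.1, equal SDs for the change term, and a baseline unaffected by allocation, which the documents do not yet guarantee.

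A reader might infer that the t-test is wrong or the trial underpowered. Neither follows: the test is valid, and 91 per arm and 230 in total reproduce.

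**What to change.** 1. State consistently in the Summary and Sections 4.a and 7.c when the pre-surgery QoR-15 is completed, so that it precedes the patient's knowledge of allocation.
2. In Section 9.a, name one primary analysis: the day-7 QoR-15 mean difference with 95% CI from a linear regression on arm, baseline QoR-15 and hospital, with missing baseline and day-7 scores handled by the multiple imputation of Section 9.d.
3. Keep the unadjusted t-test (or Mann-Whitney) as a sensitivity analysis. Move days 1 and 4 and the mixed model to the secondary endpoint of Section 7.a.ii.
4. If step 1 cannot be assured, make the hospital-adjusted day-7 difference primary and the baseline-adjusted one a sensitivity analysis.

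The cost is SAP wording, a few lines of SPSS syntax and one consistent statement of timing; no new patients or data. The downsides are three more parameters than the t-test (a baseline slope and two hospital terms), the need to impute missing baselines, and reliance on a baseline that allocation has not influenced.

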### b. Secondary study parameter(s)

Postoperative pain on post discharge day 1, 4 and 7: Mean, Standard Deviation, Mixed effects linear regression models will be conducted to investigate the effect of the smartphone app on postoperative pain over the first week post discharge as a function of the randomization assignment (i.e. intervention vs control), time (i.e. measurements before surgery, and at day 1, 4 and 7 post discharge), and their interaction term. Random effects, i.e. random intercept, will be fitted per individual to account for clustering effects

Post discharge Nausea and Vomiting (PDNV) on post discharge day 1, 4 and 7: Mean, Standard Deviation and Mixed effects linear regression models will be conducted to investigate the effect of the smartphone app on PDNV over the first week post discharge as a function of the randomization assignment (i.e. intervention vs control), time (i.e. measurements before surgery, and at day 1, 4 and 7 post discharge), and their interaction

term. Random effects, i.e. random intercept, will be fitted per individual to account for clustering effects

Medication Dosage and usage measured in morphine equivalents on post discharge day 1, 4 and 7: Mean, Standard Deviation and Mixed effects linear regression models will be conducted to investigate the effect of the smartphone app on medication dosage and usage over the first week post discharge as a function of the randomization assignment (i.e. intervention vs control), time (i.e. measurements before surgery, and at day 1, 4 and 7 post discharge), and their interaction term. Random effects, i.e. random intercept, will be fitted per individual to account for clustering effects

Difference in the number contacts with the hospital, general practitioner or emergency department (on day 7 post discharge): Mean and Standard Deviation and two sample-t-test (in case of non-normally distributed data we will report on medians and interquartile ranges and differences will be tested using the Mann-Whitney U test)

Difference in the number of surgical complications assessed according to the Clavien Dindo classification of surgical complications (on day 7 post discharge): Mean, Standard Deviation and two sample-t-test (in case of not normally distributed data we will use the Mann-Whitney U test)

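### The mixed models use only a random intercept over four visits, so their standard errors may be too small or too large; an unstructured covariance removes the assumption at little cost

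*Combined protocol and SAP*

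**What the plan says.** The main endpoint (section 7a.i) is QoR-15 "at day 7 post discharge between patients with remote monitoring (intervention group) and patients without remote monitoring". Section 9a names two analyses for it. The first compares the arms at days 1, 4 and 7 "using Student's t-test or a nonparametric Mann Whitney U test". The second is a linear mixed model for the first week after discharge, with arm, "time (i.e. measurements before surgery, and at day 1, 4 and 7 post discharge), and their interaction term". For the within-patient structure it says only: "Random effects, i.e. random intercept, will be fitted per individual to account for clustering effects". It also says that "the factor hospital will be added as fixed effect to the mixed model".

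Section 9b uses the same random intercept for pain, PDNV and medication, again over "time (i.e. measurements before surgery, and at day 1, 4 and 7 post discharge"). For these three outcomes the mixed model is the only inferential method named.

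No random slope, residual covariance structure, visit-specific variance or robust standard error is named. The one safeguard in section 9a is conditional and undefined: "we will perform a sensitivity analysis if the results of the mixed model analysis indicate for bias".

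**The concern.** A single random intercept with independent, constant-variance residuals is compound symmetry: every visit has the same variance and every pair of visits the same correlation. Here the visits run from a pre-surgery score, through the day after discharge, to a week of recovery, and they are unevenly spaced. The plan gives no reason to expect one SD and one correlation across those states.

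If the assumption fails, the fixed-effect estimates with complete data and categorical time are unchanged, but their standard errors rest on quantities averaged over visits. Confidence intervals and p-values may then be too narrow or too wide. For pain, PDNV and medication no other test is planned alongside the model. The safeguard may not help, because its trigger is bias in the results, whereas with complete data a wrong covariance affects the standard error and not the estimate.

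**Working it through.** **The plan's own figure.** Section 3d (sample size) uses a difference of 8.0, SD 19.1, two-sided alpha 0.05 and a two-sample t-test. The noncentral t gives power 0.798 with 90 per group and 0.802 with 91, so 91 reproduces. Allowing for 20% dropout, 91/0.8 = 113.75, that is 114 per group or 228 in total, close to the stated 230. None of this uses the mixed model.

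**Inputs.** The SD of 19.1 comes from section 3d and is taken as the day-7 SD; n = 91 per arm. All other SDs and all correlations are assumptions. AR(1) here means decay per successive visit.

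**Formulas (complete data, categorical time).** Let Vm be the mean of the four visit variances and Cm the mean of the six between-visit covariances. The random-intercept model in effect estimates these two quantities.

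- Day-7 arm difference: model SE = sqrt(2 Vm/n); correct SE = sqrt(2 V7/n). Correlations drop out.
- Arm-by-time contrast (day 7 minus baseline): model SE = sqrt(4(Vm − Cm)/n); correct SE = sqrt(2(V0 + V7 − 2 C07)/n).
- Type I error = 2Φ(−1.96 × model SE/correct SE).

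**Example 1: equal SDs of 19.1, AR(1) 0.7.** The variance is 364.81. The mean correlation is (3×0.7 + 2×0.49 + 0.343)/6 = 0.5705, so Cm = 208.12; C07 = 0.343 × 364.81 = 125.13. For the arm-by-time contrast, model SE = sqrt(4 × 156.69/91) = 2.62 and correct SE = sqrt(2 × (729.62 − 250.26)/91) = 3.25. The ratio is 0.81 and type I error 11.3%. For the day-7 difference both SEs are sqrt(2 × 364.81/91) = 2.83, ratio 1.00.

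**Example 2: SDs 15/25/22/19.1, constant correlation 0.5.** Vm = (225 + 625 + 484 + 364.81)/4 = 424.70; Cm = 203.27; C07 = 0.5 × 15 × 19.1 = 143.25. For the arm-by-time contrast, model SE = sqrt(4 × 221.43/91) = 3.12 and correct SE = sqrt(2 × 303.31/91) = 2.58. The ratio is 1.21 and type I error 1.8%. For the day-7 difference, 3.06 against 2.83 gives a ratio of 1.08 and 3.4%.

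**Results (model SE/correct SE, type I error in brackets).**

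| SDs: before/day 1/day 4/day 7 | Correlation | Day 7 minus baseline | Plain day-7 difference |
|---|---|---|---|
| 19.1 at all visits | AR(1) 0.6 to 0.8 | 0.83 to 0.79 (10.3% to 12.4%) | 1.00 (5.0%) |
| 18/24/21/19.1 | constant 0.5 | 1.12 (2.8%) | 1.08 (3.4%) |
| 15/25/22/19.1 | constant 0.5 | 1.21 (1.8%) | 1.08 (3.4%) |
| 15/22/20/19.1 | constant 0.5 | 1.12 (2.9%) | 1.00 (4.9%) |
| the three unequal sets above | AR(1) 0.6 to 0.8 | 0.88 to 1.00 (8.6% to 5.1%) | 1.00 to 1.08 (4.9% to 3.4%) |
| 12/17/18/19.1 | constant 0.5 | 1.02 (4.6%) | 0.88 (8.6%) |
| 15/15/15/19.1 | constant 0.5 | 0.93 (6.7%) | 0.84 (9.8%) |
| 25/25/25/19.1 | constant 0.5 | 1.05 (3.9%) | 1.24 (1.5%) |

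The two rows where the plain day-7 ratio is below 1 have a day-7 variance above the average: 364.81 against (144 + 289 + 324 + 364.81)/4 = 280.45, and against (3 × 225 + 364.81)/4 = 259.95.

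**Check of the formulas.** REML random-intercept fits to 100 simulated trials in each of four scenarios gave mean model SEs within about 0.02 of the formula values.

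**The case against.** The strongest reply is that the endpoint is the arm difference on day 7, and section 9a already tests it with a t-test or Mann-Whitney test. That test uses day-7 data alone and makes no assumption about other visits. The sample size rests on the t-test too: "An 8.0 difference in the overall score in the QoR-15 questionnaire on postoperative day 7" is its target. This stands.

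A reader might infer from the 10 to 12% figure that the day-7 comparison itself has an inflated type I error. The documents do not support that. The figure belongs to the day-7-minus-baseline contrast with equal SDs and decaying correlations; in those same scenarios the plain day-7 difference has exactly 5%. Its standard error becomes too small only if day 7 is more variable than the average visit, and nothing in the documents indicates that.

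It is also fair to say that unequal SDs and decaying correlations, if both occur, partly cancel: the ratio for the arm-by-time contrast then lies between 0.88 and 1.00 in the scenarios above. And the plan does not state the residual structure, so compound symmetry follows from the usual default and not from explicit wording. A reader should therefore not conclude that the intervals are known to be wrong, only that they may be.

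Three things remain. The plan does not say whether the t-test or the mixed model decides the day-7 question, and only the latter adjusts for hospital, the randomisation stratum. Pain, PDNV and medication have no alternative test. And cancellation cannot be relied on in advance.

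**Conclusion.** The point holds as an avoidable modelling restriction, not as a demonstrated error in the primary result. Under the assumed SDs and correlations, the QoR-15 model's arm-by-time contrast may have a standard error from about 21% too small to 21% too large, with much smaller errors when the two departures offset each other. The plain day-7 difference is at most 8% too conservative on the SD sets with the largest spread on day 1; it reaches 0.84 or 1.24 only if day 7 stands well apart from all other visits.

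Direction and size cannot be determined from the documents. No SDs or correlations are given for pain, PDNV or medication, so the same mechanism applies there without a figure. With missing data a wrong covariance can also affect the estimates, and the multiple imputation planned in section 9d does not relax the assumption in the analysis model.

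**What to change.** In sections 9a and 9b, for all four mixed models (QoR-15, pain, PDNV, medication):

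- treat time as categorical;
- replace the random intercept with an unstructured within-patient covariance over the visits, fitted by REML with Satterthwaite degrees of freedom;
- name the fallback covariance structure to be used if the model does not converge;
- state that the day-7 arm difference, with its confidence interval, is the contrast reported from the model.

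The hospital term in the QoR-15 model stays as it is. An unstructured covariance over four visits has 4 variances and 6 covariances, ten parameters in place of two, which 182 (2 × 91) to 230 patients can readily support. No extra data or patients are needed; the cost is SAP wording.
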